## 9.6 DATA MANAGEMENT

The data will be entered by the investigators themselves and/or authorized personnel directly in the electronic case report form (eCRF). A Data Management Plan (DMP) will be prepared to describe all functions, processes, and specifications for data collection, cleaning and validation.

Data Management will be performed by the CRO . This contract organization will be responsible for the development and implementation of the data management plan and preparation of the data handling report according to the sponsor's standards.

The database will be housed in a physically and logically secure computer system maintained in accordance with a written security policy. The system will meet the standards of the International Committee on Harmonization guideline E6R1 regarding electronic study data handling. Patient confidentiality will be strictly maintained.

Once the study has been completed and all data from the last patient have been recorded, the database will be closed and statistical analysis will be performed.

## 9.7 DATA ANALYSIS

The proposed methods for statistical analysis presented below are a summary of the methods that will be applied in the study to analyse the data collected and to answer the study objectives. Missing data will not be imputed in the main analysis (but eventually in sensitivity analyses as deemed appropriate). When applicable, the presence of potential outliers will be indicated. Analysis will primarily be performed including these outliers. However, excluding the respective patients in sensitivity analyses might be a reasonable approach to assess the impact of these outliers.

Analyses will be performed by the CRO . Since the study is essentially descriptive the variables included in the study objectives will be analysed with measures of central tendency (mean and median), variability/dispersion (standard deviation and

interquartile ranges), absolute and relative frequencies, and ranges. 95% confidence intervals will be provided as appropriate.

Missing values and data not available in the charts will be displayed in separate categories.

All the analyses will be performed using the Statistical Package for the Social Sciences (SPSS), version 22.

#### **9.7.1 Main analysis**

For the primary objective absolute and relative frequencies of patients across different lung function categories will be calculated.

For the secondary objectives:

To describe demographic and clinical baseline characteristics of IPF patients at time of treatment initiation with nintedanib (OFEV®) and prevalence of comorbidities, descriptive statistics and confidence interval at 95% will be calculated for the key variables defined. For the quantitative variables the number of evaluable patients and the measures of central tendency and dispersion (median, the standard deviation, the median, Q1 and Q3) will be obtained, and for the qualitative variables the absolute and relative frequencies relative to the total of patients and to the total of patients with data (total percentage and valid percentage, respectively) will be obtained.

For the secondary objective to describe the distribution of patients based on reimbursement threshold, absolute and relative frequencies of patients across different lung function categories will be calculated.

#### **9.8 QUALITY CONTROL**

To improve and secure data quality, automatic data checks upon data entry will be done within the eCRF. In the eCRF, plausible ranges of values for numeric data entries as well as logical data entries and listings will be provided for each entry field. Based on this, checks on completeness and plausibility will be performed upon data entry in the eCRF.

Validity of data entry thus is ensured by integrated validation checks performed by the system, indicating missing or implausible entries to the document list or investigator. All corrections will be visible from the system audit trail.

No regular source data verification is planned in this study. However, in case of decreasing compliance (i.e. of missing data, data discrepancies, protocol violations, etc.) a for-cause audit or risk-based monitoring visit may be performed.

In addition, a quality assurance audit/inspection of study may be conducted by the sponsor or sponsor's designees or by Independent Ethics Committee (IECs) or by regulatory authorities. The quality assurance auditor will have access to all medical records, the investigator's study-related files and correspondence, and the informed consent document (if applicable).

## **9.9 LIMITATIONS OF THE RESEARCH METHODS**

A non-interventional study is the most suitable design to obtain information about the use of medicines in everyday therapeutic practice and thus for investigating questions regarding routine clinical practice.

The selection criteria are less restrictive than the ones of a randomized clinical trial, which will permit the enrolment of a broader patient population. The choice of nintedanib (OFEV®) therapy will have been done before the study initiation at the discretion of the investigator. However, as the study is limited to the hospital setting, patients treated in other clinical settings may not be part of the sample. In addition only patients initiating nintedanib (OFEV®) will be described and no information on IPF patients not initiating this treatment or on other treatments will be collected in this study. This has the limitation that it is not feasible to put the results into perspective to IPF patients initiating other kinds of treatments.

Another limitation is that data in medical records may have missing values and could reduce the validity of conclusions. However, the parameters collected in this study are those most frequently collected for IPF in real-world practice.

Precision of estimates could be improved with a higher sample size. However as it was stated in the sample size justification, provided an acceptable accuracy, and considering the scarce prevalence of the disease, it is a representative number of patients.

Finally, due to the cross-sectional study design no conclusion on any causal association could be drawn.

## **9.10 OTHER ASPECTS**

The study will be initiated only after all required legal documentation has been reviewed and approved by the respective IEC and competent authority (CA) according to national and international regulations. The IEC/CA will be notified about the end of the study (last patient included) or early termination of the study.

## **9.11 SUBJECTS**

Approximately 175 IPF patients from 35 Pulmonology Services in Spain are planned to be included in the study.

To be eligible to participate in the study, patients must meet the following selection criteria.

**Inclusion criteria:**

Patients could be included in the study if all of the following criteria are met:

1. The patient is at least 18 years old
2. The patient has IPF diagnosis according to most recent ATS/ERS/JRS/ALAT IPF guideline for diagnosis and management [\[5\]](#)
3. The patient newly initiated treatment with nintedanib (OFEV®) since 01 January 2016 up to end of data collection date, according to the approved local SmPC.

**Exclusion criteria:**

Patients will be excluded if the following criterion is met:

1. Patients treated with nintedanib within a clinical trial or named-patient program or with any prior treatment of nintedanib.

### **9.11.1 Withdrawal criteria**

Not applicable. Retrospective chart review, with no direct contact to patients. See section 10.

## **9.12 BIAS**

In order to ensure representativeness of patients among the whole country, each Investigator will include 5 patients. To minimize selection bias, a simple randomization will be applied. The Investigator will share an anonymized list of all of patients who meet selection criteria with the CRO. The list will include the minimum patient data to be identifiable by the investigator, for example, age, gender and treatment initiation date. Then, CRO will generate a random sequence of the 5 patients to be included and will inform the Investigator.

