On June 2014 a named-patient use (NPU) program of nintedanib started in Spain offering the treatment to the same type of patients than in clinical trials (%FVC $>50$ ). Afterwards, on September 2014, pirfenidone was available on the market in Spain, for IPF patients with FVC between 50-80%. Therefore, nintedanib NPU program was limited to patients not responding to pirfenidone, or when pirfenidone was not reimbursed (FVC  $>80\%$ ), or with emphysema and/or not clear IUP pattern. On 15 January 2015, nintedanib (OFEV®) obtained the EU approval for all IPF patients and NPU program in Spain was also offered to all patients independent of their %FVC. On December 2015, OFEV® was finally available with reimbursement in Spain and nintedanib NPU program ended. Compared to pirfenidone, nintedanib reimbursement is not restricted based on FVC% predicted level.

There is no available data on nintedanib use in routine clinical practice. For this reason, this retrospective chart review is proposed to characterize clinical profile of IPF patients treated with nintedanib (OFEV®) during routine clinical practice in Spain.

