## 9. RESEARCH METHODS

### 9.1 STUDY DESIGN

This non-interventional study, based on medical charts, will be conducted in approximately 35 Pulmonology Services of Hospitals in Spain. IPF patients will be characterized at time of nintedanib initiation (cross-sectional study design).

The participating investigators will review their IPF patient's medical records since 01 January 2016 up to the end of data collection date and identify all IPF patients who initiated nintedanib (OFEV®) during that time. To minimize selection bias, a simple randomization will be applied. The Investigator will share an anonymized list of all of patients who meet selection criteria with the CRO. The list will include the minimum patient data to be identifiable by the investigator, for example, age, gender and treatment initiation date. Then, CRO will generate a random sequence of the 5 patients to be included and will inform the Investigator.

As this is a non-interventional study, designed to reflect real-world clinical practice, the decision to start treatment with OFEV® is prior to and independent of the selection of the patient in the study and based on routine clinical practice and medical judgment criteria. In addition, no intervention, either diagnostic or therapeutic, will be applied to patients other than that used for routine clinical practice.

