## 9.4 DATA SOURCES

Data collection will be limited to those available in the medical records of selected patients. All medical records of the 35 included centers will be screened for IPF patients and then patients who initiated treatment with nintedanib since 01 January 2016 up to the end of data collection date will be identified. 5 patients per site will be selected based on a simple randomization of all the patients from each physician.

Demographics and comorbidities will be obtained from the available information of patient's medical records on the date of treatment initiation.

Most of data will be available in the charts but as a routine clinical practice, some data could be missing. However, it will be recorded in the CRF if data for the respective variables was not available. Data will be included in an eCRF by investigators.

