Section 11: Data management and quality control	Yes	No	N/A	Section Number
11.3 Is there a system in place for independent review of study results?				

Comments:

Section 12: Limitations	Yes	No	N/A	Section Number
12.1 Does the protocol discuss the impact on the study results of:				
12.1.1 Selection bias?				9.12
12.1.2 Information bias?				9.9
12.1.3 Residual/unmeasured confounding? (e.g. anticipated direction and magnitude of such biases, validation sub-study, use of validation and external data, analytical methods)				
12.2 Does the protocol discuss study feasibility? (e.g. study size, anticipated exposure, duration of follow-up in a cohort study, patient recruitment)				9.5

Comments:

This study is only descriptive

Section 13: Ethical issues	Yes	No	N/A	Section Number
13.1 Have requirements of Ethics Committee/ Institutional Review Board been described?				10
13.2 Has any outcome of an ethical review procedure been addressed?				
13.3 Have data protection requirements been described?				10

Comments:

Section 14: Amendments and deviations	Yes	No	N/A	Section Number
14.1 Does the protocol include a section to document amendments and deviations?				5

Comments:

Section 15: Plans for communication of study results	Yes	No	N/A	Section Number
15.1 Are plans described for communicating study results (e.g. to regulatory authorities)?				12

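### An equal quota of 5 patients per investigator spreads the sample across sites; it does not make it representative of nintedanib starters, and the protocol plans no check of the effect on the primary percentages

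*Combined protocol and SAP*

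**What the plan says.** Section 9.12 (Bias) gives the quota its purpose: "In order to ensure representativeness of patients among the whole country, each Investigator will include 5 patients". Section 9.11 gives the totals: "Approximately 175 IPF patients from 35 Pulmonology Services in Spain are planned to be included in the study". Section 9.4 describes the draw: "5 patients per site will be selected based on a simple randomization of all the patients from each physician". Sections 9.1 and 9.12 say how it is done: "The Investigator will share an anonymized list of all of patients who meet selection criteria with the CRO", and the CRO then picks the 5 at random.

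The aim in section 7 concerns patients: "this retrospective chart review is proposed to characterize clinical profile of IPF patients treated with nintedanib". The primary analysis in 9.7.1 is unweighted: "For the primary objective absolute and relative frequencies of patients across different lung function categories will be calculated". Section 9.7 names optional sensitivity analyses for missing data and for outliers only.

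Section 9.2 chooses sites by trial experience, named-patient programme experience and access to the drug. Section 9.9 (Limitations) mentions the restriction to hospitals, but neither the equal quota nor this choice of sites. In Annex 2, checklist item 7.2.1 cites 9.12 as addressing selection bias. Item 12.1.1, under the question "12.1 Does the protocol discuss the impact on the study results of", cites 9.12 again.

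**The concern.** The random draw protects against selection within a list. It does nothing about selection between lists: every site contributes 5 patients whether it has 5 starters or 40. The pooled percentage therefore gives each site equal weight, while the stated aim is the profile of treated patients.

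A reader told that the quota ensures representativeness will take the FVC and DLCO category percentages as those of nintedanib starters in Spain. Even for starters on the participating sites' lists, that needs list length and lung function to be unrelated. Section 9.3.1 gives a reason to doubt it for FVC: some regions limit reimbursement by %FVC, which could affect both how many patients start and which categories they fall in. This makes a link plausible; it does not show one.

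The checklist treats the matter as dealt with, but 9.12 contains only the quota and the draw, and says nothing about impact on the results.

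**Working it through.** **The plan's own figures.** 35 × 5 = 175 patients; 175 × 0.9 = 157.5, rounded to 158 (9.5). The Wald half-width 1.96 × √(p(1−p)/158) is 7.80 points at p = 79/158 and 4.28 at p = 13/158. These match the stated ±7.8 and ±4.3.

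**What the quota estimates.** Let site i list Mᵢ eligible patients, of whom a fraction pᵢ is in a given category. If every Mᵢ is at least 5, the unweighted percentage estimates the mean of pᵢ over sites. The distribution over listed starters is ΣMᵢpᵢ/ΣMᵢ. The first minus the second is −cov(M, p)/mean(M), which is zero if list lengths are equal or unrelated to pᵢ.

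**Illustration with assumed inputs.** The documents give no Mᵢ or pᵢ. Take two kinds of site: a share f of large sites (10, 12 or 17 of 35), volume ratio R (2, 4 or 6), and prevalence difference d (5, 10 or 20 points). Large sites hold a share s = fR/(fR + 1 − f) of all starters but only f of the sample, so |bias| = d × (s − f).

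For f = 10/35:

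| R | s − f | d = 5 | d = 10 | d = 20 |
|---|---|---|---|---|
| 2 | 0.159 | 0.8 | 1.6 | 3.2 |
| 4 | 0.330 | 1.6 | 3.3 | 6.6 |
| 6 | 0.420 | 2.1 | 4.2 | 8.4 |

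Check of the covariance form: 10 lists of 20 with 55% and 25 lists of 5 with 45% give 47.86% unweighted and 51.15% patient-weighted, a gap of 3.30 points. The formula gives 30.61/9.286 = 3.30.

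Over all three values of f the range is 0.79 to 8.40 points. Bias reaches half the planned half-width (3.9 points) when d = 3.9/(s − f): 23 to 25 points at R = 2, 12 to 13 at R = 4, 9 to 11 at R = 6.

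**Small category.** With 4% in one kind of site and 12% in the other (d = 8), the bias is 1.3 to 3.4 points. The expected sample percentage is 6.3% to 9.7%, with half-width 3.8 to 4.6, so the bias is 27% to 89% of the matching half-width.

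**Lists shorter than 5.** With 25 lists of 3 and 10 lists of 12, the sample is 25×3 + 10×5 = 125. Large sites supply 50/125 = 40.0% of it and hold 120/195 = 61.5% of starters. The difference of 0.215 gives 1.1, 2.2 and 4.3 points for d = 5, 10 and 20: a smaller sample and a smaller bias.

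**Price of weighting.** The Kish factor (fR² + 1 − f)/(fR + 1 − f)² gives intervals 5.5–6.1% wider at R = 2, 17–24% at R = 4 and 24–37% at R = 6. The mean squared errors with and without weights are equal at d = √(p(1−p)/n)/√(f(1−f)), whatever R is: 8.0 to 8.8 points at p = 0.5 and 4.4 to 4.8 at p = 13/158. With f = 10/35, p = 0.5, 4.5 evaluable patients per site and an assumed site ICC of 0.05 or 0.10, it is about 9.5 or 10.2 points.

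**The case against.** The strongest reply is that the sentence is about geography. It refers to the whole country, the abstract says sites will be spread across Spain, and a quota does stop a few large centres from supplying most of the sample. Selection bias is assigned to a separate device, the random draw, which works within each list. That is a fair reading of the intent. The sentence still claims representativeness of patients, which geographic spread does not give.

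Second, the analysis methods in 9.7 are called a summary and Annex 1 lists a stand-alone SAP, so weights may exist there. Section 10 also says that site and investigator characteristics will be captured. This limits the finding on weights to the protocol. It does not repair the wording of 9.12, the silence of 9.9 or the checklist entries, and section 10 does not name list length.

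Third, every driver of the magnitude is assumed. In 19 of the 27 combinations the bias is below 3.9 points, and in only 2 (both at R = 6, d = 20) does it exceed 7.8. The reimbursement limits concern %FVC and say nothing about DLCO or list length. All of this stands, as does the fact that weighting increases mean squared error when large and small sites differ little. It argues for a sensitivity analysis, not a new main analysis. Nor can weighting correct the purposive choice of sites, which has to be disclosed.

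Finally, 9.12 says investigator while 9.4 says both site and physician. Since 35 × 5 = 175, one list per site fits the totals, and taking M as the length of the list sent to the CRO makes the unit explicit.

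**Conclusion.** The concern holds. That an equal quota does not ensure representativeness of patients follows from the selection probabilities, with no assumed numbers. The size is not known: zero bias fits the documents, and 0.8 to 8.4 points is what the assumed two-size model gives with f from 10/35 to 17/35, R from 2 to 6 and d from 5 to 20. A material effect needs sizeable volume ratios together with lung function that differs by site size. The absence of weights is shown for the protocol only. This should be corrected, because the primary percentages can be misread and the information needed for a check already reaches the CRO. It does not invalidate the planned main analysis or the planned N of 175.

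**What to change.** 1. Replace the first sentence of 9.12, for example: *Five patients per site are selected at random within site to obtain geographic spread; the selection probability is min(1, 5/Mᵢ), where Mᵢ is the length of the list sent to the CRO, and differs between sites.*
2. Record Mᵢ at the time of each draw.
3. Keep the unweighted frequencies as the main analysis. Pre-specify one sensitivity analysis: FVC and DLCO category percentages among patients with data, each patient weighted by Mᵢ divided by the number evaluable for that outcome at that site, with site-clustered intervals. FVC and DLCO weights may differ. A site with no evaluable patient is left out for that outcome, and the share of listed starters not covered is reported. The rule in 9.7, "Missing values and data not available in the charts will be displayed in separate categories", continues to apply to the unweighted table.
4. Add the equal quota and the purposive choice of sites to 9.9. State that weighted figures apply only to starters on the participating sites' lists and assume data are missing at random within site.

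Sites with none of 5 patients evaluable should be rare. At 20% or 30% missing, 35 × 0.2⁵ = 0.01 or 35 × 0.3⁵ = 0.09 are expected if missingness is independent, and 0.8 or 1.7 under an assumed within-site correlation of 0.3 (beta-binomial).

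The cost is short wording changes in 9.12 and 9.9, one number per list and one table. The weighted intervals will be wider, by about 5% to 37% under the assumed volume ratios, which is why the unweighted result should lead.

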## **10. PROTECTION OF HUMAN SUBJECTS**

The study will be carried out in compliance with the protocol, the principles laid down in the Declaration of Helsinki, current legislation in Spain concerning the conduct of observational studies (Orden SAS/3470/2009), relevant BI Standard Operating Procedures (SOPs) and following Good Epidemiological Practice Guideline (GEP) and the guideline for good pharmacoepidemiological practice (GPP).

The study will be initiated only after all required legal documentation has been reviewed and approved by the respective IEC and CA according to national regulations. The same applies for the implementation of changes introduced by protocol amendments.

Retrospective observational studies can be exempt from a written informed consent per local regulations and legal requirements, IRB / IEC often grants a waiver of consent for retrospective chart review studies. In order to avoid bias by exclusion of subjects that cannot be given informed consent for any reason like death, missing contact information etc., exempt from a written informed consent should be asked to Ethics Committees for such situations.

In case such a waiver is not given, prior to patient participation in the study, written informed consent must be obtained from each patient (or the patient's legally accepted representative) according to ICH GCP and to the regulatory and legal requirements of the participating country. Each signature must be personally dated by each signatory and the informed consent and any additional patient-information form retained by the investigator as part of the study records. A signed copy of the informed consent and any additional patient information must be given to each patient or the patient's legally accepted representative.

The patient must be informed that his/her personal study-related data will be used by BI in accordance with the local data protection law (Organic Law 15/1999 of 13 December on the Protection of Personal Data). The level of disclosure must also be explained to the patient.

The patient must be informed that his/her medical records may be examined by Clinical Quality Assurance auditors appointed by BI, by appropriate IEC members, and by inspectors from regulatory authorities.

The investigator should inform the sponsor immediately of any urgent safety measures taken to protect the study subjects against any immediate hazard, and also of any serious breaches of the protocol.

eCRF will be provided by the CRO via remote data capture. All of the clinical data and site/investigator characteristics will be captured via a web-based Electronic Data Capture (EDC) system. The site staff will enter and edit the data via a secure network, with secure access features (username, password and secure identification – an electronic password system). A complete electronic audit trail will be maintained.

Individual patient medical information obtained as a result of this study is considered confidential. Patients must not be identified on the eCRF by name. Appropriately coded identification (i.e. Patient numbers) must be used. Any supporting documentation must be redacted of any patient identifying information and the patient ID number must be clearly written on the documents.

The investigator / institution will permit study-related monitoring, audits, IEC review and regulatory inspection, providing direct access to all related source data / documents. eCRFs and all source documents, including progress notes and copies of laboratory and medical test results must be available at all times for review by the sponsor's auditor and inspection by health authorities (e.g. AEMPS).

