## 9.5 STUDY SIZE

The following table illustrates the precision of estimates of the prevalence of a specific lung function profile within the population of interest depending on the observed rate of affected patients and the sample size. The dropout rate is assumed to be 10% for all scenarios.

Precision is estimated based on two-sided 95% confidence intervals.

Table 1 Precision table

N	N to be analyzed	% observed in subsample	95% CI	Precision
100	90	7.8% (7 out of 90)	[2.2; 13.3]	±5.6
150	135	8.1% (11 out of 135)	[3.5; 12.8]	±4.7
175	158	8.2% (13 out of 158)	[3.9;12.5]	±4.3
100	90	50.0% (45 out of 90)	[39.7; 60.3]	±11.3
150	135	50.4% (68 out of 135)	[41.9; 58.8]	±8.5
175	158	50.0% (79 out of 158)	[42.2;57.8]	±7.8

It can be seen that by raising the sample size from 100 to 150 patients, precision improves to less than  $\pm 5\%$  for the small sample of 8% and to less than 10% for the large sample of 50%. Precision can be further improved to less than  $\pm 4.5\%$  for the small proportion of 8% and to less than 8% for the large sample of 50% if 175 patients will be recruited.

Planning a recruitment of 175 patients allows for an acceptable precision of prevalence of a specific lung function profile (see section 9.3.2.1) estimates.

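### Does section 10's written-consent fallback contradict section 9.11.1 and bias the severity distribution by losing patients who died before chart review?

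*Combined protocol and SAP*

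**What the plan says.** Section 9.11.1 deals with withdrawal in one line: "Not applicable. Retrospective chart review, with no direct contact to patients. See section 10". Section 10 observes that retrospective chart reviews can be exempt from written consent and often are. It gives the reason for seeking exemption, "In order to avoid bias by exclusion of subjects that cannot be given informed consent for any reason like death" or missing contact details, and the action: "exempt from a written informed consent should be asked to Ethics Committees for such situations". Only if the waiver is not given does the fallback apply: "prior to patient participation in the study, written informed consent must be obtained from each patient (or the patient's legally accepted representative".

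Sections 9.1 and 9.12 describe the selection. "The Investigator will share an anonymized list of all of patients who meet selection criteria with the CRO"; then "CRO will generate a random sequence of the 5 patients to be included and will inform the Investigator". Section 9.12 adds that "each Investigator will include 5 patients". With 35 sites this makes the planned 175. The inclusion and exclusion criteria in section 9.11 do not exclude patients who have died.

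Section 9.5 states that "The dropout rate is assumed to be 10% for all scenarios" and does not define dropout. Section 9.7.1 plans frequencies for the primary objective. Section 9.9 does not list consent among the limitations. Annex 1 lists the SAP and the Data Management Plan as stand-alone documents; neither text was available for this review.

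**The concern.** Read together, the sections seem to conflict. A signature means contact, and a person asked to sign may refuse or later withdraw. Section 9.11.1 allows for neither, and its cross-reference leads to the text that requires the signature.

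There is also an operational gap. If a drawn patient has died or cannot be reached at a site that needs consent, the protocol does not say whether that patient is dropped, replaced or counted. The instruction to include 5 could be taken as an invitation to substitute. A substitute chosen by the site and not recorded would undo the random draw.

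The stake is the primary outcome. Section 9.3.2.1 takes its severity categories from a stratification based partly on survival differences, and section 7 puts median survival at around three years. Loss through death could therefore fall more heavily on the severe categories and understate their share.

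**Working it through.** **1. Is there a contradiction?** There are two cases.

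- Exemption granted: there is no contact, section 9.11.1 is correct as written, and deceased patients stay in the draw.
- Exemption refused: section 10 governs, and section 9.11.1 already points to it. Contact takes place, a representative may sign, and only patients with no obtainable consent are lost.

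The statement in 9.11.1 describes the default. The conflict arises only in the second case, and there the cross-reference leads to the rule that applies.

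**2. The plan's own precision.** From section 9.5, N = 175 and 175 × 0.90 = 157.5, shown as 158. The half-width is 1.96 × √(p(1−p)/n).

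- 13/158 = 8.2%: 1.96 × √(0.0823 × 0.9177/158) = 4.3 points, as stated.
- 79/158 = 50%: 1.96 × √(0.25/158) = 7.8 points, as stated.

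The protocol does not say that either proportion is the severe share. Using them that way is an assumption.

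**3. How many deaths before extraction?** Assumptions: treatment starts are spread evenly over the 20 months from January 2016 to the start of data collection (September 2017), charts are read at month 22, and survival is exponential. Time at risk T is then uniform on 2 to 22 months. With monthly hazard h, the mean probability of death is 1 − (e^(−2h) − e^(−22h))/(20h).

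- Median 3 years (section 7, counted here from treatment start): h = ln 2/36 = 0.01925, giving 0.201, or 1.01 of 5 per site.
- Median 5 years (assumed as the favourable end): h = ln 2/60 = 0.01155, giving 0.127, or 0.64 of 5 per site.

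**4. Shift in the severe share.** Let s be the true severe share, HR the hazard ratio of severe to other patients, h0 = h/(s·HR + 1 − s) the hazard in the others, and f the fraction of sites that need consent. Ss and So are the retained fractions of severe and other patients. Each is the mean survival probability plus a fraction r of the deaths, kept through a representative. Without replacement,

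observed share = s(1−f+f·Ss) / [s(1−f+f·Ss) + (1−s)(1−f+f·So)].

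Neither HR (1.5 to 3) nor r (0 or 0.5) is in the protocol; both are assumed. The low end uses 5 years, HR 1.5 and r = 0.5. The high end uses 3 years, HR 3 and r = 0.

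| Sites needing consent | True 8%: understated by | True 50%: understated by |
|---|---|---|
| none | 0 | 0 |
| 7 of 35 (f = 0.2) | 0.04 to 0.4 points | 0.1 to 0.9 points |
| half (f = 0.5) | 0.1 to 1.0 points | 0.3 to 2.4 points |
| all (f = 1) | 0.2 to 2.3 points | 0.6 to 5.4 points |

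Worked high end for 8% and all sites: Ss = 0.573 and So = 0.823, so the observed share is 0.08 × 0.573/(0.08 × 0.573 + 0.92 × 0.823) = 5.7%, a shift of 2.3 points. Every entry is smaller than the planned half-width (4.3 or 7.8).

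**5. Would a drawn-versus-included count repair it?** With D drawn, k not included and x severe among those included, the severe share among the drawn lies between x/D and (x+k)/D.

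- 7 lost, 13 severe of 168 included: 13/175 = 7.4% to 20/175 = 11.4%.
- 17 lost, 13 severe of 158 included: 7.4% to 30/175 = 17.1%. This is 9.7 points wide, against 2 × 4.3 = 8.6 for the whole planned interval.
- Charts may also lack FVC or DLCO, which section 9.4 expects for some data. If 17 of the 168 had no value (an assumption), the first upper limit becomes (13+7+17)/175 = 21.1%.
- Refusals and unreachable patients add to k. With 7 consent-only sites (35 drawn patients), the deaths in step 3 and 10% to 30% of living patients lost (assumed), k is 7.5 to 15.4 and the range is 4.3 to 8.8 points wide.

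The range would have to be given twice, once for FVC and once for DLCO. It bounds the bias and does not remove it.

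**The case for a change.** The best case for a change is that the sponsor named this bias, yet section 9.9 omits it and section 9.12, on selection bias, does not mention consent. Section 10 speaks of ethics committees in the plural, so waiver status may differ between sites. The CRO holds the list and the draw, so a tally costs little, whereas an unrecorded substitution cannot be reconstructed afterwards. Under a 3-year median, deaths alone would use up the 10% dropout allowance once about 17 sites needed consent (0.10/0.201 × 35 = 17.4); under 5 years, about 27. A shift of 2.3 points on a true 8% is also a large relative error, and lying inside the half-width does not make a bias harmless.

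Part of this stands. Handling of a drawn patient without obtainable consent is unwritten, and the 10% dropout is undefined. But the protocol has the CRO, not the site, fix which patients are included, and nothing in it invites a site to choose a substitute. A disposition count and any use of further random numbers are ordinary detail for the SAP or Data Management Plan. The larger shifts need refusal at every site together with the extreme assumptions, although section 10 regards waivers as commonly granted.

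A stronger remedy would ask committees to release category counts for drawn patients who were not included. That seeks data on people without consent from a committee that has just required it, so it is not a dependable gain.

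**Conclusion.** No change is needed. Sections 9.11.1 and 10 are in tension only where an exemption is refused, and the cross-reference resolves which section then governs. Patients who have died are not left without a provision: section 10 identifies the bias, plans the exemption request and allows a representative to sign. The remaining gap is the bookkeeping of drawn patients for whom consent cannot be obtained, which competent analysts would settle without protocol text.

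The effect is zero where exemptions are granted. In the illustrations, deaths shift the severe share by 0.04 to 2.3 points at a true 8%, and by 0.1 to 5.4 points at a true 50%. These figures rest on exponential survival, medians of 3 to 5 years counted from treatment start, hazard ratios of 1.5 to 3, no replacement and losses through death only. The protocol supplies only the 3-year median, so the actual size cannot be estimated. A worst-case range would add little: it is narrow only when few patients are lost and values are nearly complete, and it becomes wider than the planned interval when losses reach the assumed 10%.
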